11.2.6 Immune-Related Best Overall Response Using irRC (irBOR)

irBOR is the best confirmed overall response over the study as a whole, recorded between the date of first dose until the last tumor assessment before subsequent therapy (except for local palliative radiotherapy for painful bone lesions) for the individual subject in the study. For the assessment of irBOR, all available assessments per subject are considered.

irCR or irPR determinations included in the irBOR assessment must be confirmed by a second (confirmatory) evaluation meeting the criteria for response and performed no less than 4 weeks after the criteria for response are first met.

12 DATA REPORTING / REGULATORY REQUIREMENTS

Adverse event lists, guidelines, and instructions for AE reporting can be found in Section 7.0 (Adverse Events: List and Reporting Requirements).

12.1 Data Reporting

12.1.1 Method

The Office of Data Quality (ODQ) will collect, manage, and perform quality checks on the data for this study.

12.1.2 Responsibility for Data Submission

Investigative sites within DF/HCC or DF/PCC are responsible for submitting data and/or data forms to the Office of Data Quality (ODQ) in accordance with DF/HCC policies.

12.2 Data Safety Monitoring

The DF/HCC Data and Safety Monitoring Committee (DSMC) will review and monitor toxicity and accrual data from this study. The committee is composed of medical oncologists, research nurses, pharmacists and biostatisticians with direct experience in cancer clinical research. Information that raises any questions about participant safety will be addressed with the Overall PI and study team.

The DSMC will review each protocol up to four times a year with the frequency determined by the outcome of previous reviews. Information to be provided to the committee may include: up-to-date participant accrual; current dose level information; DLT information; all grade 2 or higher unexpected adverse events that have been reported; summary of all deaths occurring within 30 days of intervention for Phase I or II protocols; for gene therapy protocols, summary of all deaths while being treated and during active follow-up; any response information; audit results, and a summary provided by the study team. Other information (e.g. scans, laboratory values) will be provided upon request.

12.3 Multi-Center Guidelines

This protocol will adhere to DF/HCC Policy MULTI-100 and the requirements of the DF/HCC Multi-Center Data and Safety Monitoring Plan. The specific responsibilities of the Sponsor-Investigator, Coordinating Center, and Participating Institutions and the procedures for auditing are presented in Appendix D.

13 ETHICAL ASPECTS

13.1 Local Regulations

The study must fully adhere to the principles outlined in “Guideline for Good Clinical Practice” (GCP) ICH E6 Tripartite Guideline (January 1997). The investigator will ensure that the conduct of the study complies with the basic principles of GCP as outlined in the current version of 21 Code of Federal Regulations, subpart D, Part 312, “Responsibilities of Sponsors and Investigators” Part 50, “Protection of Human Subjects” and Part 56, “Institutional Review Boards.”

13.2 Informed Consent

It is the responsibility of the investigator, or a person designated by the investigator, to obtain written informed consent from each subject participating in this study after adequate explanation of the aims, methods, anticipated benefits, and potential hazards of the study. In the case where the subject is unable to read, an impartial witness should be present during the entire informed consent discussion. After the subject has orally consented to participation in the trial, the

witness's signature on the form will attest that the information in the consent form was accurately explained and understood.

If new safety information results in significant changes in the risk/benefit assessment, the consent form should be reviewed and updated as necessary. All subjects (including those already being treated) should be informed of the new information, should be given a copy of the revised form, and should give their consent to continue in the study.

13.3 Institutional Review Board/Ethics Committee

This study is being conducted under a United States Investigational New Drug application or other Clinical Trial Application, as appropriate. This protocol (and any modifications) and appropriate consent procedures must be reviewed and approved by an IRB/EC. This board must operate in accordance with current local, regional, and federal regulations. The investigator will send a letter or certificate of IRB/EC approval to Exelixis (or designee) before subject enrollment and whenever subsequent modifications to the protocol are made.

14 CONDITIONS FOR MODIFYING THE PROTOCOL

Protocol modifications (including protocol amendments) may be made and will be prepared, reviewed, and approved by representatives of the investigator. Protocol modifications or amendments must be reviewed and approved by Exelixis and Bristol Myers Squibb prior to implementation.

All protocol modifications must be submitted to the IRB/EC for information and approval in accordance with local requirements and to regulatory agencies if required. Approval must be obtained before any changes can be implemented, except for changes necessary to eliminate an immediate hazard to study subjects or those that involve only logistical or administrative aspects of the trial (eg, change in monitor or change of telephone number).

15 CONDITIONS FOR TERMINATING THE STUDY

At any time, the study may be terminated by the study sponsor(s), the sponsoring institution, or by Exelixis and/or Bristol Myers Squibb. Should this be necessary, Exelixis and/or Bristol Myers Squibb and the investigator will arrange the procedures on an individual study basis after review and consultation. In terminating the study, Exelixis and/or Bristol Myers Squibb and the investigator will ensure that adequate consideration is given to the protection of the subjects' interests. Upon study termination, the investigator(s) shall cease enrolling subjects into the study, and shall discontinue conduct of the study as soon as is medically practicable.

15.1 Collaborative Agreements Language

N/A

16 STATISTICAL CONSIDERATIONS

16.1 Study Design/Endpoints

The study intends to examine the clinical efficacy and tolerability of cabozantinib and nivolumab in the treatment of patients with advanced carcinoid. The study includes an interim analysis after 18 patients to assure tolerability and to evaluate response rate of combining cabozantinib and nivolumab. This combination is likely to be well tolerated based on prior studies in patients with breast cancer and renal cell carcinoma, but these data require confirmation in patients with carcinoid tumors. This is a one-arm study without randomization. If objectives of the interim analysis are met then enrollment will be expanded to include 17 additional patients.

16.1.1 Primary endpoint:

The primary efficacy endpoint is the objective response rate (ORR) in patients with advanced carcinoid tumors treated with the combination of cabozantinib and nivolumab. ORR is defined using the RECIST 1.1 criteria as the proportion of subjects with a confirmed CR or a confirmed PR.

16.1.2 Secondary endpoint:

The secondary endpoints are safety, response rate according to immune-related response criteria, duration of response, progression free survival (PFS), and overall survival (OS) for patients with advanced carcinoid tumors treated with the combination of cabozantinib and nivolumab.

16.2 Sample Size, Accrual Rate and Study Duration

The primary objective of this study is to investigate the safety and tolerability of the combination of cabozantinib and nivolumab. Based on the results of a phase II trial of cabozantinib as monotherapy for patients with advanced carcinoid and pancreatic NET and other trials examining anti-PD-1 agents in patients with other malignancies not selected by PD-L1 status, a true objective response rate (ORR) of 10% or less would not be of clinical interest and represents the null hypothesis of this study. A true rate of 30% would be considered a clinically meaningful level of response. The sample size for this study was chosen to have 95% power to declare the combination effective at this rate with a one-sided Type 1 error of no more than 5%.

Using a Simon's two-stage design, 18 patients will be enrolled in the first stage. If in this first stage there are at least 3 patients with an objective response (ORR), accrual will continue to the second stage where an additional 17 patients will be enrolled. If there are at least 7 patients with an objective response among the total 35 patients, the regimen will be considered worthy of further study.

If the true response rate is 10%, the chance the regimen is declared worthy of further study is less than 5% (exact alpha = 0.047). If the true response rate is 30%, the chance that the regimen is declared worthy of further study is 95%

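### The two-stage rule in section 16.2 has 90.2% power at a 30% response rate, not the stated 95%, so the risk of missing an active regimen is about twice what is stated

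*Combined protocol and SAP*

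**What the plan says.** Section 16.2 gives everything needed to work out the operating characteristics.

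- Null: "a true objective response rate (ORR) of 10% or less would not be of clinical interest and represents the null hypothesis of this study".
- Alternative: "A true rate of 30% would be considered a clinically meaningful level of response".
- Error limit: a "one-sided Type 1 error of no more than 5"%.
- Stage 1: "18 patients will be enrolled in the first stage".
- Continuation: "If in this first stage there are at least 3 patients with an objective response (ORR), accrual will continue to the second stage". Section 16.4 repeats this rule.
- Stage 2 and success: 17 more patients; at least 7 responses among 35 count as success.

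It then reports the results. For type I error it gives "exact alpha = 0.047". For power it gives 95% twice, first as the design target ("The sample size for this study was chosen to have 95% power to declare the combination effective at this rate") and then as a property of the rule ("If the true response rate is 30%, the chance that the regimen is declared worthy of further study is 95"%).

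**The concern.** The alpha and the power are quoted for one and the same rule, so both should come out of one calculation. Only the alpha does.

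The primary endpoint is ORR, and power is the stated reason for enrolling 35 patients. It also informs how a negative result is read. If the trial fails, a reader relying on section 16.2 would put the chance of having missed a regimen with a 30% ORR at 1 in 20, when under the written rule it is about 1 in 10. The wrong figure would also carry over into any report that quotes the design.

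**Working it through.** **Inputs** (all from section 16.2): p0 = 0.10, p1 = 0.30, n1 = 18, continue if X1 ≥ 3, n2 = 17, success if X1 + X2 ≥ 7.

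**Formula.** With X1 ~ Bin(18, p) and X2 ~ Bin(17, p) independent,

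P(success | p) = Σ over x = 3 to 18 of P(X1 = x) × P(X2 ≥ 7 − x).

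For x ≥ 7 the second factor is 1.

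**Step 1: reproduce the stated alpha (p = 0.10).**

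| X1 | P(X1) | P(X2 ≥ 7 − X1) | Product |
|---|---|---|---|
| 3 | 0.1680 | 0.0826 | 0.0139 |
| 4 | 0.0700 | 0.2382 | 0.0167 |
| 5 | 0.0218 | 0.5182 | 0.0113 |
| 6 | 0.0052 | 0.8332 | 0.0044 |
| ≥ 7 | 0.0012 | 1 | 0.0012 |

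The sum before rounding is 0.0474. This agrees with the stated 0.047, so this is the rule the plan evaluated.

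**Step 2: power by the same formula (p = 0.30).**

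| X1 | P(X1) | P(X2 ≥ 7 − X1) | Product |
|---|---|---|---|
| 3 | 0.1046 | 0.7981 | 0.0835 |
| 4 | 0.1681 | 0.9226 | 0.1551 |
| 5 | 0.2017 | 0.9807 | 0.1978 |
| 6 | 0.1873 | 0.9977 | 0.1869 |
| ≥ 7 | 0.2783 | 1 | 0.2783 |

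The sum is **0.9016**, against a stated 0.95. The shortfall is 0.95 − 0.9016 = 0.048, or 4.8 points. The miss risk is 1 − 0.9016 = 0.0984, and 0.0984 / 0.05 = 1.97.

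**Step 3: stage-1 stopping.**

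- At p = 0.10, P(X1 ≤ 2) = 0.734. The expected sample size is 18 + 17 × (1 − 0.734) ≈ 22.5.
- At p = 0.30, P(X1 ≤ 2) = 0.0600. This alone exceeds the 5% miss risk that 95% power allows, so with this stage-1 rule no final cut-off can reach 95%.

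**Step 4: can another reading give 95%?** All variants use 35 patients in total.

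| Variant | Alpha | Power at 30% |
|---|---|---|
| No interim look, ≥ 7 of 35 | 0.0552 | 0.935 |
| Continue on ≥ 2, success on ≥ 7 | 0.0537 | 0.930 |
| Continue on ≥ 3, success on ≥ 6 | 0.1009 | 0.928 |
| Continue on ≥ 3, success on ≥ 8 | 0.0184 | 0.846 |
| Continue on ≥ 4 (Schema wording), success on ≥ 7 | 0.0335 | 0.818 |

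None gives 95% power, and none gives the stated alpha. A normal approximation for a single stage of 35 at one-sided 5% gives 0.934. The written rule gives 0.947 at a true ORR of 33% and 0.952 at 33.5%, so it reaches 95% only between those rates.

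**Step 5: what 95% would need.** With alpha at most 5%, a search over two-stage designs found a smallest total of 41 patients: 25 in stage 1, continue on ≥ 3, success on ≥ 8 of 41 (alpha 0.047, power 0.951). A single stage with ≥ 8 of 41 gives alpha 0.048 and power 0.954. For a 90% target, a search over totals up to 37 returns exactly the written 18/35 design as the one with the smallest expected sample size under the null.

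**The case against.** There is no defence of the 95% itself. The fair objections concern scope, remedy and weight.

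- **More than one stage-1 rule.** The Schema asks for more than 3 responses before expansion, while sections 16.2 and 16.4 ask for at least 3. The 90.2% belongs to the second rule only. This stands as a separate conflict to reconcile. It does not help the stated power, which would fall to 81.8% under the Schema wording. Only the 16.2/16.4 rule reproduces the stated alpha.
- **Which figure is the slip?** The plan may have meant 90%, or it may have meant 95% and ended up with too few patients. It does not say. The matching alpha and the fit of 18/35 to a 90% target point to a slip for 90%, but that is inference.
- **Limited harm.** Type I error is controlled, 90% is adequate power, and power enters neither the success count nor the confidence interval. After a negative result, the observed rate and its interval carry most of the interpretation. This is fair: the trial's validity is not threatened. Even so, a stated property of the primary analysis is wrong.
- **Denominator.** Section 11.1.1 restricts response evaluability to patients with at least one cycle and a reassessment (early progression excepted), and section 16.2 has no dropout allowance. The 90.2% therefore assumes that all enrolled patients count. This stands as a caveat.

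**Conclusion.** The concern holds. For the rule in sections 16.2 and 16.4, power at a true ORR of 30% is 90.2%, not 95%, and the type II error is 9.8%, not 5%. The stated alpha is correct. The result rests on independent binomial responses, on all 18 and then all 35 patients being counted, and on continuation at 3 or more responses. The difference is too large for rounding and is not removed by ignoring the interim look. The text must be corrected; the design can stand if 90% is the intended power.

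**What to change.** In section 16.2, change both statements of 95% power at an ORR of 30% to 90% (exact 0.902). Add the probabilities of stopping at stage 1: 73.4% at an ORR of 10% and 6.0% at 30%. State that these figures apply to continuation on at least 3 of 18 with all enrolled patients counted, and bring the Schema into line with sections 16.2 and 16.4.

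The cost is two figures and a sentence or two of text. Sample size and the section 16.2 decision rule do not change, and no patients are added; the price is a less favourable stated power. The sponsor should confirm that 90% was intended. If 95% was a real requirement, correcting the text is not enough, because the smallest two-stage design found needs 41 patients, 6 more than the planned 35.

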16.3 Analysis Plan

The primary endpoint is the objective response rate (ORR). We will calculate the frequency and percentage of responses. The point estimate of the ORR with a 9% confidence interval based on the exact binomial distribution will be presented.

With a sample size of 35, if the observed ORR is 30%, we will estimate the 95% confidence interval for the ORR to be 14.8% to 45.2%.

Below is a table for the 95% CIs corresponding to varying observed ORR

	95% CI
15%	3.2% to 26.8%
20%	6.8% to 33.3%
30%	14.8% to 45.2%
40%	23.8% to 56.2%

The secondary endpoints are safety, response rate according to immune-related response criteria, duration of response, progression free survival (PFS), and overall survival (OS) for patients with advanced carcinoid tumors treated with the combination of cabozantinib and nivolumab.

Safety will be assessed by analysis of adverse event (AE) and toxicity data. AE and toxicity data, including laboratory values, will be graded using CTCAE version 5.0. Tabulations of toxicities will be provided by organ system and attribution.

Response rate according to immune-related response criteria will be analyzed using the same method for ORR. Duration of response will be summarized using mean, standard deviation, median, and inter-quartile range.

Progression free survival and overall survival will be defined from time of randomization to time of progression or date of death, respectively. Any patients who have not died by the analysis cut-off date or are lost to follow up will be censored at their last date of contact. Any patient that withdraws consent for follow up will be censored on the date of withdrawal of consent. Kaplan-Meier method will be employed to obtain survival estimates and median survival times will be provided. Greenwood's formula will be used to construct 95% confidence intervals around these estimates.

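### Section 16.3 prints a 9% level and names the exact binomial method for the ORR interval, but its example and table are normal-approximation 95% limits, two of the four rows at rates that 35 patients cannot give

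*Combined protocol and SAP*

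**What the plan says.** Section 16.3 (Analysis Plan) states the level and the method for the ORR interval once: "The point estimate of the ORR with a 9% confidence interval based on the exact binomial distribution will be presented". It continues with a worked example for 35 patients at a response rate of 30%: "we will estimate the 95% confidence interval for the ORR to be 14.8% to 45.2". It then introduces a table: "Below is a table for the 95% CIs corresponding to varying observed ORR". The column is headed 95% CI and the rows are:

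| Observed ORR | Printed limits |
|---|---|
| 15% | 3.2% to 26.8% |
| 20% | 6.8% to 33.3% |
| 30% | 14.8% to 45.2% |
| 40% | 23.8% to 56.2% |

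The secondary irRC endpoint follows the same rule: "Response rate according to immune-related response criteria will be analyzed using the same method for ORR".

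Section 16.2 sets the decisions as counts. On continuation after 18 patients: "If in this first stage there are at least 3 patients with an objective response (ORR), accrual will continue to the second stage". For success the plan requires "at least 7 patients with an objective response among the total 35 patients". No other section gives a level or method for the ORR interval.

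**The concern.** Three things in the same few lines do not agree.

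- The level is printed as 9%, while the next sentence, the table introduction and the column heading all use 95%.
- The method named is the exact binomial, but the printed limits are symmetric about the observed rate. Exact limits at these rates are not.
- Two of the four rates, including the one in the worked example, are not a whole number of patients out of 35. No exact interval exists for them.

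What is at stake is the stated precision of the primary endpoint and an unambiguous choice of interval before the data are seen. A programmer who checks code against the plan's table would find that the named method fails to match and that an unnamed one matches. The two can say different things about the 10% null rate of Section 16.2, as the result at 8/35 below shows.

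**Working it through.** **Inputs.** n = 35, the four rates and the printed limits come from Section 16.3. The two-stage rule comes from Section 16.2: 18 patients, continue with at least 3 responders, 17 more, success with at least 7 of 35.

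**1. Reproducing the printed figures.** Normal approximation: p ± 1.96·√(p(1−p)/35).

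| p | 1.96 × standard error | Computed | Printed |
|---|---|---|---|
| 0.15 | 1.96·√(0.1275/35) = 0.1183 | 3.17 to 26.83 | 3.2 to 26.8 |
| 0.20 | 1.96·√(0.16/35) = 0.1325 | 6.75 to 33.25 | 6.8 to 33.3 |
| 0.30 | 1.96·√(0.21/35) = 0.1518 | 14.82 to 45.18 | 14.8 to 45.2 |
| 0.40 | 1.96·√(0.24/35) = 0.1623 | 23.77 to 56.23 | 23.8 to 56.2 |

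Every limit matches to one decimal except the lower limit at 20% (6.748, printed as 6.8), which is a rounding slip. Wilson, Agresti-Coull and Jeffreys limits do not match. At 20%, for example, Wilson gives 10.04 to 35.89.

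**2. Attainability.** 0.15 × 35 = 5.25 and 0.30 × 35 = 10.5 are not whole patients. 0.20 × 35 = 7 and 0.40 × 35 = 14 are.

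**3. The method the plan names.** For x responders, the Clopper-Pearson lower limit is the 2.5% quantile of Beta(x, 36−x) and the upper limit is the 97.5% quantile of Beta(x+1, 35−x).

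| x/35 | Rate | Normal approximation | Exact |
|---|---|---|---|
| 5 | 14.3% | 2.7 to 25.9 | 4.8 to 30.3 |
| 7 | 20.0% | 6.7 to 33.3 (printed 6.8 to 33.3) | 8.4 to 36.9 |
| 8 | 22.9% | 8.9 to 36.8 | 10.4 to 40.1 |
| 10 | 28.6% | 13.6 to 43.5 | 14.6 to 46.3 |
| 11 | 31.4% | 16.0 to 46.8 | 16.9 to 49.3 |
| 14 | 40.0% | 23.8 to 56.2 | 23.9 to 57.9 |

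Width at 7/35: printed 33.3 − 6.8 = 26.5 points, exact 36.9 − 8.4 = 28.5. Width at 14/35: printed 56.2 − 23.8 = 32.4, exact 57.9 − 23.9 = 34.0. The largest gap in a single limit at a printed, attainable rate is 36.9 − 33.3 = 3.6 points, at 7/35. At 8/35 the normal approximation includes 10% and the exact interval excludes it.

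**4. A literal 9% level.** The exact 9% interval at 7/35 would be about 18.1% to 22.5%, which is plainly not intended.

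**5. Coverage if the table's method were used.** For each true rate, sum the probabilities of all outcomes whose 95% interval contains that rate. In the two-stage rows, a trial stopped at stage 1 is assumed to report its interval with n = 18.

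| True ORR | 10% | 20% | 30% |
|---|---|---|---|
| Fixed 35, normal approximation | 87.1% | 92.5% | 91.9% |
| Fixed 35, exact | 98.0% | 96.7% | 97.5% |
| Two-stage, normal approximation | 84.4% | 88.2% | 88.6% |
| Two-stage, exact | 98.2% | 96.8% | 96.7% |
| Two-stage, interval wholly below the true rate, normal approximation (nominal 2.5%) | 15.0% | 10.4% | 9.8% |
| Same, exact | 0% | 1.8% | 1.7% |

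With a fixed 35 patients, the misses of the normal approximation that lie wholly below the true rate are 12.2, 6.1 and 6.5 points out of totals of 12.9, 7.5 and 8.1. The Schema words the continuation rule as more than 3 responders. With continuation at 4 or more, two-stage coverage is 84.5%, 88.7% and 90.7% for the normal approximation and 98.5%, 96.8% and 96.9% for the exact method.

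**The case against.** The strongest reply is that the plan already commits to the exact method and that the table only illustrates. If the sentence is followed, no reported interval will under-cover, so the coverage loss is hypothetical. That is correct: the coverage figures apply only if the analyst follows the table instead of the text.

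The two-stage coverage figures also depend heavily on trials stopped at 18 patients, a case the table does not address. The 15.0% at a true rate of 10% is simply the chance of no responders in 18 (0.9^18 = 0.150), where the normal approximation collapses to a zero-width interval. Among trials that reach 35 patients, the normal approximation covers 97.7%, 97.3% and 94.2%. This is a fair caution against leaning on the two-stage figures. The fixed-35 figures involve no stage-1 stop, however, and they still show under-coverage with most misses on the low side.

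The other points concern weight. The 9% is an obvious slip and could even be a character lost when the PDF was read. The method mismatch does not depend on it. Round rates are common in planning tables: 30% is the target rate in Section 16.2, and 15% is the cabozantinib monotherapy rate in Section 2.1.2. That explains the choice, but exact limits still need whole counts. Finally, continuation and success are decided by counts, and at 7/35 both intervals include 10%. No decision turns on the table.

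**Conclusion.** The concern holds. Section 16.3 misstates the precision of the primary endpoint for the method it names. At the two attainable rows the printed intervals are narrower than the exact ones by 2.0 points (7/35) and 1.6 points (14/35), and they sit too low. At 14/35 nearly all of the difference is in the upper limit. The other two rows describe results that cannot be observed with 35 patients.

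Reading the level as 95% rests on the surrounding text. The documents do not strictly exclude 90%, so the sponsor should confirm it in writing. The coverage loss is conditional on the table's method being used. The effect is on reporting and on pre-specification of the interval, not on the design. It should be corrected before the analysis.

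**What to change.** In Section 16.3, change 9% to 95% and keep the exact binomial method. Naming it as Clopper-Pearson would remove any doubt. Replace the worked example and the table with exact 95% limits at whole counts:

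| Responders/35 | ORR | Exact 95% CI |
|---|---|---|
| 5 | 14.3% | 4.8% to 30.3% |
| 7 | 20.0% | 8.4% to 36.9% |
| 8 | 22.9% | 10.4% to 40.1% |
| 10 | 28.6% | 14.6% to 46.3% |
| 11 | 31.4% | 16.9% to 49.3% |
| 14 | 40.0% | 23.9% to 57.9% |

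Either 10/35 or 11/35 can serve as the worked example near 30%. The irRC response rate needs no edit of its own, because its cross-reference to the ORR method carries the correction over.

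The cost is one corrected figure, one example and one table. The stated intervals become slightly wider and move upward. The sample size, the stage-1 rule and the success rule of at least 7 of 35 stay as they are.

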5.6 Duration of Follow Up

Participants will be followed for initiation of a new regimen of anti-neoplastic therapy, first disease progression event after removal from protocol therapy or until death . Tumor assessments should continue to be performed every 12 weeks on these participants until first disease progression event or until death, whichever occurs first.

Participants removed from protocol therapy for unacceptable adverse event(s) will be followed until resolution or stabilization of the adverse event.

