11.1.4.4 Evaluation of Best Overall Response

The best overall response is the best response recorded from the start of the treatment until disease progression/recurrence (taking as reference for progressive disease the smallest measurements recorded since the treatment started). The patient's best response assignment will depend on the achievement of both measurement and confirmation criteria.

For Participants with Measurable Disease (i.e., Target Disease)

Target Lesions	Non-Target Lesions	New Lesions	Overall Response	Best Overall Response when Confirmation is Required*
CR	CR	No	CR	≥ 4 wks Confirmation**
CR	Non-CR/Non-PD	No	PR	
CR	Not evaluated	No	PR	
PR	Non-CR/Non-PD/not evaluated	No	PR	

SD	Non-CR/Non-PD/not evaluated	No	SD	Documented at least once ≥ 4 wks from baseline**
PD	Any	Yes or No	PD	no prior SD, PR or CR
Any	PD***	Yes or No	PD	
Any	Any	Yes	PD	

* See RECIST 1.1 manuscript for further details on what is evidence of a new lesion. ** Only for non-randomized trials with response as primary endpoint. *** In exceptional circumstances, unequivocal progression in non-target lesions may be accepted as disease progression.
 
Note: Participants with a global deterioration of health status requiring discontinuation of treatment without objective evidence of disease progression at that time should be reported as “symptomatic deterioration.” Every effort should be made to document the objective progression even after discontinuation of treatment.
				

For Participants with Non-Measurable Disease (i.e., Non-Target Disease)

Non-Target Lesions	New Lesions	Overall Response
CR	No	CR
Non-CR/non-PD	No	Non-CR/non-PD*
Not all evaluated	No	not evaluated
Unequivocal PD	Yes or No	PD
Any	Yes	PD

* ‘Non-CR/non-PD’ is preferred over ‘stable disease’ for non-target disease since SD is increasingly used as an endpoint for assessment of efficacy in some trials so to assign this category when no lesions can be measured is not advised
		

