11.1.5 Duration of Response

Duration of overall response: The duration of overall response is measured from the time measurement criteria are met for CR or PR (whichever is first recorded) until the first date that recurrent or progressive disease is objectively documented (taking as reference for progressive disease the smallest measurements recorded since the treatment started, or death due to any cause. Participants without events reported are censored at the last disease evaluation).

Duration of overall complete response: The duration of overall CR is measured from the time measurement criteria are first met for CR until the first date that progressive disease is objectively documented, or death due to any cause. Participants without events reported are censored at the last disease evaluation.

Duration of stable disease: Stable disease is measured from the start of the treatment until the criteria for progression are met, taking as reference the smallest measurements recorded since the treatment started, including the baseline measurements.

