11.1.6 Survival and Time to Progression Definitions

Overall Survival: Overall Survival (OS) is defined as the time from randomization (or registration) to death due to any cause, or censored at date last known alive.

Progression-Free Survival: Progression-Free Survival (PFS) is defined as the time from randomization (or registration) to the earlier of progression or death due to any cause. Participants alive without disease progression are censored at date of last disease evaluation.

Time to Progression: Time to Progression (TTP) is defined as the time from randomization (or registration) to progression, or censored at date of last disease evaluation for those without progression reported.

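### Section 16.3 makes progression the only PFS event, while section 11.1.6 also counts death; followed as written, 16.3 overstates PFS on average if patients die without documented progression

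*Combined protocol and SAP*

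**What the plan says.** The Analysis Plan (16.3) defines both time-to-event endpoints in one sentence: "Progression free survival and overall survival will be defined from time of randomization to time of progression or date of death, respectively". It then says that those "who have not died by the analysis cut-off date or are lost to follow up will be censored at their last date of contact", and that a patient who withdraws consent for follow-up is censored on the withdrawal date. Estimation is by Kaplan-Meier, with medians reported.

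Section 11.1.6 defines three endpoints separately:

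- **PFS** runs "to the earlier of progression or death due to any cause". For censoring: "Participants alive without disease progression are censored at date of last disease evaluation".
- **TTP** has progression as its only event, "or censored at date of last disease evaluation for those without progression reported".
- **OS** ends at death from any cause, with censoring when the patient was last known to be alive.

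Section 11.1.5 ends duration of response at recurrence, progression or "death due to any cause. Participants without events reported are censored at the last disease evaluation".

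PFS is a secondary objective (1.3.4) and a secondary endpoint (16.1.2). TTP appears in neither list. Section 16.1 describes a one-arm study with no randomization.

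**The concern.** The two sections give PFS different events. In its event, the PFS of 16.3 is the TTP of 11.1.6, an endpoint the study does not claim to report. Section 16.3 does not refer to 11.1.6, and no section takes precedence.

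Section 16.3 also leaves open what happens to a patient who dies before progression: it gives no censoring date. Its last-contact sentence concerns patients who have not died, so it reads most naturally as an OS rule, and 16.3 then has no PFS censoring rule at all. If the sentence were applied to PFS, it would conflict with censoring at the last disease evaluation in 11.1.6.

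The definitions are also inconsistent with each other. A responder who dies without progression would end duration of response but would have no PFS event.

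At stake is a PFS curve that tends to flatter the regimen, in a trial with no control arm in which the error could cancel. Two standing definitions also allow the choice to be made after the results are seen.

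**Working it through.** The documents state no PFS median, rate or event count, so there is no figure of the plan's own to reproduce. The check covers direction first, then size.

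**1. Direction, deaths censored at the death date.** Hold all other censoring the same. At every event time the two rules then have the same number at risk, and 11.1.6 has at least as many events. Each Kaplan-Meier factor under progression-only is therefore equal to or larger than the one under 11.1.6, so the progression-only curve can never lie below.

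**2. Direction, deaths censored at the last disease evaluation (the TTP rule).** The curve can dip briefly. Take five patients: one is scanned at week 7 and dies at week 10, one progresses at week 8, and three continue.

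- At week 8, 11.1.6 has five at risk and one event: 4/5 = 0.80.
- At week 8, progression-only has four at risk and one event: 3/4 = 0.75.
- After week 10, 11.1.6 falls to 0.80 × 3/4 = 0.60, while progression-only stays at 0.75.

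**3. Closed form for the median.** Assume constant hazards λp (progression) and λd (death without progression), continuous observation and death-date censoring. Let f = λd/(λp + λd). The PFS median is ln 2/(λp + λd) and the progression-only median is ln 2/λp, so the ratio is 1/(1 − f):

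- f = 5%: 1/0.95 = 1.05
- f = 10%: 1/0.90 = 1.11
- f = 20%: 1/0.80 = 1.25

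**4. Simulation on the protocol's schedule.** From the documents: 35 patients (5.1); scans at weeks 8, 16 and 24, then every 12 weeks, each within ±1 week (section 10 and 11.1). Assumed: 18-month accrual plus 12 months of follow-up, true median PFS of 12 or 18 months, and f of 5, 10 or 20%. There were 2,000 trials per row. Mean 12-month estimates:

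| True median (months) | f | 11.1.6 PFS | Progression only, deaths censored at death | Progression only, deaths censored at last scan | Excess (points) |
|---|---|---|---|---|---|
| 12 | 5% | 0.524 | 0.542 | 0.540 | 1.8 / 1.6 |
| 12 | 10% | 0.523 | 0.559 | 0.557 | 3.6 / 3.4 |
| 12 | 20% | 0.517 | 0.590 | 0.586 | 7.3 / 6.9 |
| 18 | 5% | 0.648 | 0.663 | 0.662 | 1.5 / 1.4 |
| 18 | 10% | 0.645 | 0.675 | 0.674 | 3.0 / 2.9 |
| 18 | 20% | 0.645 | 0.707 | 0.705 | 6.2 / 6.0 |

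At f = 10% there are about 2 such deaths among 18 to 23 events. The typical estimated median then moves only from 13.7 to 13.9 months, or from 19.2 to 19.5. At f = 20% it moves from 13.6 to 16.4, or from 19.1 to 22.1.

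With death-date censoring the curve was below 11.1.6 in 0% of trials, as step 1 requires. With last-scan censoring it was below at some time in 30 to 46% of trials, typically by at most 0.2 points (95th percentile 0.6 to 0.9). The median came out earlier in at most 0.3%.

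**5. Different assumptions.** With a progression median of 18 months, administrative censoring uniform over 12 to 36 months and scans exactly on schedule, 12-month values under 11.1.6 and progression-only were 0.639 and 0.655 (f = 5%), 0.621 and 0.654 (10%), and 0.580 and 0.651 (20%). The excess is 1.6, 3.3 and 7.1 points.

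**6. Last-contact censoring, only if it were applied to PFS.** With f = 0, replacing last-scan by last-contact censoring adds 0.3 to 0.4 points to 12-month PFS when no scans are missed. It adds 1.7 to 2.1 points if 10% of patients stop scans while contact continues, and 2.9 to 3.8 points if 20% do. Those shares are assumed.

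**The case against.** The strongest reply is that the intended definition can be recovered. Section 11.1.6 is the definitions section and separates PFS from TTP, so the authors knew the difference. Duration of response counts death, and follow-up in 5.6 runs to progression or death. The sentence in 16.3 also speaks of randomization in a one-arm study, so it looks like template wording. A statistician might well apply 11.1.6 unprompted, with no effect on the results. This is plausible, but it asks the analyst to set aside a stated rule in the Analysis Plan, and it does not make that rule correct.

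The protocol also limits the deaths that matter. Off treatment, "Tumor assessments should continue to be performed every 12 weeks on these participants", and after symptomatic deterioration, "Every effort should be made to document the objective progression even after discontinuation of treatment". So f may be small or zero. This stands.

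The closed-form inflation also overstates what the scan schedule would show: at f = 10% the simulated median moves about 1.5% (0.2/13.7), not 11%. This stands too, and the simulated values are the better guide.

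The bias is modest against the precision of 35 patients. The standard error of a 12-month estimate near 0.52 is about √(0.52 × 0.48/35) = 0.084, a 95% half-width of about 17 points. The excess at f = 10% is about a fifth of that. This limits the practical weight, but the bias tends to run one way and can be avoided.

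Finally, if the last-contact sentence is an OS rule, the PFS censoring problem shrinks to a missing cross-reference. That is accepted; the step 6 figures apply only on the less natural reading and carry no weight in the conclusion.

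**Conclusion.** Section 16.3 is wrong as written and should be corrected. Its PFS event contradicts 11.1.6, and following it overstates PFS on average whenever patients die without documented progression. If nobody does, this bias is zero. Under the assumptions in the working, mean 12-month PFS is inflated by 1.4 to 1.8 points at f = 5%, 2.9 to 3.6 at 10% and 6.0 to 7.3 at 20%; a clear shift in the typical median appears only at 20%. The share f, true median, accrual time and follow-up are assumptions, not document figures. The contradiction itself rests on the text alone.

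The consequence is confined to a secondary, descriptive endpoint. The ORR decision rule is untouched. The reference to randomization is a wording error and causes no bias.

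**What to change.** Before PFS is analysed, replace the definition and censoring sentences in 16.3 with the rules of 11.1.6:

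- **PFS:** from registration to progression or death from any cause, whichever comes first; patients alive and progression-free are censored at their last disease evaluation.
- **OS:** from registration to death from any cause; other patients are censored when last known to be alive.
- State that the last-contact and consent-withdrawal sentences apply to OS only, as the way of fixing the last date known alive.
- Use registration alone as the time origin in both 16.3 and 11.1.6.
- If a progression-only result is wanted, report it separately as TTP and state the censoring date used for deaths.

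The cost is two or three sentences in 16.3 and a wording edit in 11.1.6. No new data, visits or patients are needed. The one downside is that reported PFS may look slightly shorter.
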